4.1 Treatment Design

Type of Design: Open label; two group study with healthy controls

Screening/Baseline: Participants will undergo a general medical screening visit to include vital signs, physical exam and pregnancy test (if applicable), then proceed with spirometry.

Intervention/Treatment

Participants will inhale aerosolized radiolabeled sulfur colloid ($Tc99m$ -SC) and will undergo gamma scintigraphy to measure mucociliary and cough clearance (MCC/CC) of the radiolabeled particles from the airways in both groups. During the first hour of MCC imaging patients will attempt to avoid coughing. Patients will then inhale 4 puffs of albuterol (90 mcg/puff via metered dose inhaler (MDI) with spacer) to assess the effect of beta-adrenergic stimulation on MCC over the second hour of MCC

imaging. After the two hours of MCC imaging patients will perform spirometry and directed coughing over a 30 minute period during which CC will be measured, again by gamma scintigraphy. Subjects will then rest (app 3.5 hours) and be scanned for 15 minutes at 6 hour \pm 30 minutes post initial MCC/deposition scan.

Table of procedures

| PCD MCC/CC study flow sheet | minutes needed | cumulative min |
|---|----------------|----------------|
| 1 Vital signs, PE,pregnancy test, PFT | 30 | 30 |
| 2 Put Americium fiducial markers on | 5 | 35 |
| 2 Co57 Transmission scan | 5 | 40 |
| 3 Background scan | 15 | 55 |
| 4 Radioaerosol inhalation | 5 | 60 |
| 5 MCC scan (no cough) | 64 | 124 |
| 6 Albuterol MDI (4 puffs with spacer) | 6 | 130 |
| 7 MCC scan post albuterol | 54 | 184 |
| 8 PFT and directed coughing (30 coughs including any spontaneous induced by PFTs) | 20 | 204 |
| 9 CC scan post PFT/cough | 4 | 208 |
| 10 Rest until final scan 6 hours after beginning of #5 | 210 | 418 |
| 11 6 hour post initial radioaerosol MCC scan | 15 | 433 |

Unscheduled Visits: There is no expectation for unplanned visits. Subjects will simply be rescheduled if they have a change in health.

4.1. Outcome Measures

Primary Outcome(s): Baseline MCC (Ave60Clr) in subjects with PCD caused by mutations associated with mild and severe clinical phenotypes.

Secondary Outcome(s): Change in MCC (Ave120Clr-Ave60Clr) after the administration of albuterol in subjects with PCD caused by mutations associated with mild and severe clinical phenotypes PCD patients with mild disease compared to PCD patients with more severe disease.

Tertiary/Exploratory Outcome(s): Change in cough clearance (Ave150Clr-Ave120Clr) in subjects with PCD caused by mutations associated with mild and severe clinical phenotypes PCD patients with mild disease compared to PCD patients with more severe disease.

5. Study Participants

5.1. Number of Participants

Number to be recruited for screening: 40

Number of eligible participants enrolled 32

5.2. Eligibility

Inclusion Criteria for PCD Patients

1. Age 12-90 of both genders

2. Confirmed PCD diagnosis with identified genetic mutations.
3. Negative pregnancy test for females who are not s/p hysterectomy with oophorectomy.
4. FEV1 of at least 30% of predicted.

Inclusion Criteria for Healthy Controls:

1. Age \geq 18 years old.
2. Subjects must have an FVC, FEV1 and FVC/FEV1 of at least 80% of predicted. Subjects who fall out of the normal range will be offered a copy of the test to share with their personal physician.
3. No pre-existing lung disease (asthma, cystic fibrosis, etc.).
4. Negative pregnancy test for females who are not s/p hysterectomy with oophorectomy.

Exclusion Criteria for all participants:

Clinical Contra-indications:

1. Any chronic medical condition considered by the PI as a contraindication to the exposure study including significant cardiovascular disease, diabetes, chronic renal disease, chronic thyroid disease, immunodeficiency, history of tuberculosis
2. Any acute infection requiring antibiotics within 4 weeks of study.
3. Mental illness or history of drug or alcohol abuse that, in the opinion of the investigator, would interfere with the participant's ability to comply with study requirements.
4. Medications which may impact the results of the study treatment, or may interfere with any other medications potentially used in the study (to include steroids, beta antagonists, non-steroidal anti-inflammatory agents)
5. Active smoking to include e-cigarettes within 1 year of the study, or lifetime of > 10 pack years of smoking
6. History of vaping or current vaping.
7. Allergy/sensitivity to study drugs, or their formulations.
8. Viral upper respiratory tract infection within 4 weeks of challenge.
9. Radiation exposure history in the past year which would be outside the safe levels
10. **Pregnant or lactating women** will also be excluded since the risks associated with radiation are unknown and cannot be justified
11. Use of the following medications:
 - a. Use of beta blocking medications
 - b. Receipt of LAIV (Live Attenuated Influenza Vaccine), also known as FluMist, within the prior 30 days, or any vaccine within the prior 5 days
 - c. Multivitamins, Vitamin C or E or herbal medications in the 4 days prior to the treatment visit
 - d. Non-steroidal anti-inflammatory drugs in the 4 days prior to the treatment visit.
12. Known IgE mediated hypersensitivity to albuterol

13. Physical/laboratory indications:

- a. Temperature > 37.8
- b. Subjects >15 y.o - Systolic BP >150 mm hg or < 90 mm Hg or diastolic BP > 90 mm Hg or < 50 and Subjects 12-15 y.o – Systolic BP > 130 mmHg or < 80 mmHg or diastolic BP > 80 or <40
- c. Oxygen saturation of < 93%

14. Inability or unwillingness of a participant to give written informed consent.

5.3. Strategies for Recruitment and Retention

Recruitment Strategy:

We will recruit subjects who have a known diagnosis of PCD caused by mutations in genes associated with a milder clinical phenotype (RSPH1, RSPH9, RSPH4a, and DNAH11) and subjects with PCD caused by mutations in genes associated with a more severe clinical phenotype (DNAH5, DNAI1, CCDC39, and CCDC40). In addition, we will recruit healthy controls from the general public to include fliers around UNC campus, e-mails, and/or by word of mouth. PCD subjects may be recruited from pediatric or adult PCD clinics at UNC by physicians listed on the protocol including [name], [name], and [name]. In addition, subjects may have had diagnostic information obtained from other research studies completed at our institution and will be recruited from previous PCD research studies. The research studies below will provide diagnostic PCD information for patients: 98-1015 (1395), 05-2997 (5901), 05-2979 (5902), 08-0764 (5903), 10-1523 (5904), 14-1225 (5905), and 20-0508 (5906). Once patients with the above genetic mutations are identified, patients will be called by a study coordinator or a study physician to recruit subjects for the study.

Retention Strategy:

We will perform the initial screening over the phone or virtually, in order to decrease the number of in person visits required. The study is to be performed over the span of one day, and will not require follow-up, therefore it is less likely for subject to drop out.

Screen Failures:

For subjects who do not meet enrollment criteria, all study related activity will stop once it is determined that the subject does not meet criteria.

5.4. Consent Process

Once subjects have been identified, a study coordinator or physician will call the patient to present and describe the study. Due to COVID-19 pandemic, precautions to limit in person contact include using phone calls or virtual calls to explain and discuss the study. The study coordinator/physician will also review the consent form with the subjects in the same method if they agree to the study. If subject agrees, a signature for the consent form will be required on the day of the study.

For children under the age of 18, their guardian or parent will be approached in the same manner as above. After explanation of the study, the consent form will be explained to the parent or guardian. Parent or guardian will sign the consent form the day of the study. The study procedures will also be

explained to the subject in age appropriate language during the call. Written and signed assent will be obtained the day of the procedure. When reasonably available, two parent or guardians will be required to provide consent for minors to participate. For situations when a parent is available able to consent but obtaining the written signature is not feasible, DocuSign may be used to document parental permission electronically.

6. Study Intervention

6.1. Intervention – Test Article

Description: Albuterol; HFA 90 mcg/puff; 4 puffs; one time. It is available commercially as ProAir HFA or Ventolin HFA.

Formulation/Packaging/Labeling: [As supplied by manufacturer/Sponsor]

Open label study

Storage and Stability:

Albuterol MDI will be delivered to and stored at a secure location within the research office. Albuterol MDI is stable at room temperature.

Preparation and Administration:

Albuterol MDI inhaler will require a spacer to be administered. Dose is 4 puffs one time for patients of all ages.

Modification:

No anticipated modification necessary.

Accountability:

Albuterol MDI inhaler will be disposed of after the completion of the study.

6.2. Assignment Procedures

Matching and Stratification: N/A

Randomization, Concealment, and Blinding: (N/A)

Masking (Blinding): N/A

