| Objectives | 
Primary To measure mucociliary clearance (MCC) in subjects with primary ciliary dyskinesia (PCD) caused by mutations in genes associated with a milder clinical phenotype and subjects with PCD caused by mutations in genes associated with a more severe clinical phenotype. To compare the 2 groups with each other and with healthy individuals.
 
Secondary To measure the effect of a short acting beta adrenergic (SABA) on MCC in subjects with PCD caused by mutations in genes associated with a milder clinical phenotype and subjects with PCD caused by mutations in genes associated with a more severe clinical phenotype.
 
Tertiary/Exploratory To measure cough clearance in subjects with PCD caused by mutations in genes associated with a milder clinical phenotype and subjects with PCD caused by mutations in genes associated with a more severe clinical phenotype.
 |
| Target Population | 
The target population is patients with PCD having confirmed mutations in genes associated with a milder clinical phenotype and subjects with PCD caused by mutations in genes associated with a more severe clinical phenotype. Subjects for this study will be recruited based on genotype.
 
Key Inclusion Criteria
 
PCD Patients
 
1. PCD subjects with mutations in genes associated with a milder clinical phenotype. This includes subjects with 2 confirmed mutations in RSPH1, RSPH9, RSPH4a, and DNAH11. This group may also include subjects with mutations in newly identified genes that are associated with a milder clinical phenotype. OR PCD subjects with mutations associated with a more severe clinical phenotype. This includes subjects with 2 confirmed mutations in DNAH5, DNAI1, CCDC39, and CCDC40. This group may also include subjects with mutations in newly identified genes that are associated with a more severe clinical phenotype.2. Age 12 - 90 years old3. Subjects of childbearing potential must be non-pregnant and non-lactating. 
Healthy Controls
 
1. ≥ 18 years old2. No pre-existing lung disease (asthma, cystic fibrosis, etc.)4. Subjects of childbearing potential must be non-pregnant and non-lactating. |

| | |
|--|--|

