Prior to each MCC study, a transmission Co57 scan will be performed to define the lung boundaries, to assign regions of interest, and to normalize these regions for lung volume differences. A rectangular phantom containing the radioisotope Co57 (< 25 mCi) will be placed in front (5cm) of the subject sitting with his/her back to the gamma camera for 30 seconds. The transmission scan has been used by us (e.g., 05-2358, 08-0795, 06-1016, 13-1605, 15-938) and others to provide a delineation of lung boundaries for generating the central (C) and peripheral (P) regions of interest (ROIs) used to assess initial particle deposition (C/P ratio) and subsequent clearance of the inhaled radio-aerosol [15-16]. Prior to the transmission scan on each study day, we will place 2 spot markers of Americium241 (0.9 microcurie (uCi) each, gamma 66 KeV) on the upper and lower back of each subject during scanning (both Tc99m-SC deposition/retention and Co57 transmission). With dual isotope imaging, these spot markers will allow alignment of images for more accurate determination of regional deposition/retention. These very low radiation sources have been obtained from commercially available home smoke alarms. The placement of these markers will be determined to be outside the lung field during the transmission scan. Their location will be marked in semi-permanent ink for later placement during Tc99m deposition/retention scans. The shielded side of this source will be placed/taped onto the subject's skin. Radiolabeled Tc99m-sulfur colloid will be delivered using a modified Pari-LC Star nebulizer (MMAD 9.5 um). This is a closed delivery system that produces 80 ml/sec air flow, and therefore limits the inspiratory flow rate to this value. While seated in front of a gamma camera subjects will perform single inhalations lasting ~10 seconds each from the delivery system and will exhale at 500 ml/sec (using feedback from a flow meter in the breathing circuit). Approximately 5 of these inhalation maneuvers will be required to deposit an adequate isotope dose to the lung. Subjects will be allowed to breathe normally (off the nebulizer) in between each inspiratory maneuver. Each volunteer will practice these maneuvers prior to the actual radio-aerosol inhalation to guarantee his/her proficiency. The activity of Tc99m-SC loaded in the nebulizer will be adjusted to provide an estimated 40 uCi deposited in the lung for the MCC/CC scan. Patients between the age 12-18 years old will receive ¼ of the adult dose to account for the smaller lung volume. A single crystal detector will be placed at the subject's back during inhalation to monitor dose to the lung. Total inhalation time should be less than 5 minutes in all cases. Immediately following isotope inhalation, the subject will gargle and drink water to clear activity that deposited in the mouth into the stomach. The subject will then (within a minute of final inhalation maneuver) be seated in front of a large-field-of-view gamma camera to begin acquiring consecutive 2 minute images. The first two-2 minute images will provide initial, time zero activity (i.e. 100% retention) followed by the same imaging at the start of every 10-minute period until 1 hour has passed to assess baseline MCC. Subjects will then inhale 4 puffs of albuterol from the MDI inhaler and consecutive 2 min imaging continues for the next hour to assess the effect of albuterol on MCC. PFTs will then be performed and subjects will cough a total of 30 times over a 30-minute period to assess CC by gamma imaging over that period. Finally, a static 15-minute image will be measured at 6 hours (±30 minutes) after the initial radio-aerosol deposition scan. (See table of procedures in section 4.1).

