Expected results, potential problems, and alternatives. We expect to observe a significant rate of MCC (different from 0) in the group of PCD patients with mutations in genes associated with a milder phenotype. Based on previous studies of ciliary activity in PCD subjects with mutations associated with a more severe phenotype, we expect to see little or no MCC in this group of PCD patients. Further, we expect the rate of MCC to be significantly greater in subjects in the “mild genotype” group compared to the PCD patients in the “severe genotype” group. We expect that subjects with a mild genotype will respond to albuterol with an increase in MCC while the PCD patients with the severe genotype will not. We expect that subjects with mutations in genes associated with a mild phenotype will have better cough clearance compared to subjects with mutations in genes associated with a severe phenotype. As we have performed many similar studies in the past, including studies of MCC in PCD subjects, we anticipate no technical difficulties in carrying out these studies. If there is no difference detected between the groups of PCD patients, this would suggest that the less severe clinical phenotype observed in some patients is not due to the maintenance of a low level of MCC. Nevertheless, this would be an important experimental finding, as it would indicate that some other mechanism is responsible for the difference in phenotype.

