11.9. Data Handling and Record Keeping

11.9.1. Data Collection and Management Responsibilities

Monitoring Plan: We will use REDCap for data management. The data will be entered by one person (typically the coordinator or, for lab analysis, a lab staff member) and then checked by a second person. The data is not marked "complete" until the 2nd person verifies the entry. REDCap creates a data dictionary when the database is established, this is used as the codebook.

Database documentation: All databases using equipment generated have a date and user attached to the electronic file. Data will be linked with a codebook (i.e. sample ID) using Excel. A second entry is done manually in a lab notebook, which includes date, samples assayed, assay used, any issues (like missing samples/data), reference to where data is stored, and a printout of the data (all as hardcopies in a lab notebook). Adherence to the codebook is ensured by having a second individual to check the entries. The PI takes responsibility for data management computations.

Case report forms: Case report forms will be developed by the study team, using templates from previous studies. These forms are maintained by study coordinators and reviewed by investigators as needed.

How will confidentiality be maintained: Subjects will be issued a subject number when they enroll into the study, and this number will only be used to label samples. All PHI will be maintained by the study coordinator or the investigators and will be kept in locked areas when not in use. The identifiers that go into REDCap will only be accessible to those who need them for their job, specifically study physicians, investigators and coordinators. Subjects sometimes undergo procedures – such as sitting in front of the gamma camera – at the same time, however other than basic introductions, nothing about one subject is disclosed to the other subject.

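### The plan provides for neither masked nor automated scan processing, although genotype group is known in advance and clearance depends on region assignment and image alignment

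*Combined protocol and SAP*

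**What the plan says.** On masking, section 6.2 has one entry, "Masking (Blinding): N/A", next to equally blank entries for matching and randomisation. Section 4.1 describes the design as "Type of Design: Open label; two group study with healthy controls". The synopsis states "Subjects for this study will be recruited based on genotype", so group membership is known before anyone is scanned.

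On measurement, the MCC procedures in section 8 say: "Prior to each MCC study, a transmission Co57 scan will be performed to define the lung boundaries, to assign regions of interest". Two Americium markers are fixed to the back, and "these spot markers will allow alignment of images for more accurate determination of regional deposition/retention". The regions serve both the initial C/P ratio and later clearance. Section 9.1 defines clearance as 100 × (1 − retention), averaged over the 10-minute values. Section 9.3 uses C/P as a covariate in all three aims.

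On expectations, the closing part of section 9.3 says "we expect the rate of MCC to be significantly greater in subjects in the “mild genotype” group", with little or no clearance in the severe group and an albuterol response only in the mild group.

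On safeguards, section 11.8 (quality assurance and quality control) is N/A. Section 11.9.1 says "Subjects will be issued a subject number when they enroll into the study", but restricts that number to labelling samples, and section 11.4 says that no specimens are collected. The second-person check in 11.9.1 covers data entry and the codebook. It does not cover image processing.

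**The concern.** Open-label albuterol accounts for unmasked treatment. It does not prevent masked outcome assessment: a scan file can be coded and processed by someone who has not been told the genotype.

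Without randomisation, the comparison of mild, severe and healthy groups needs the outcome to be measured in the same way in each. Ave60Clr is computed from images after regions have been set and frames aligned. If the person doing this knows the group and the predicted direction, choices within the range of reasonable practice could differ by group. The same choices feed C/P, so covariate adjustment cannot be relied on to remove the effect.

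The planned clearance values in the PCD groups are small, so a shift that would be trivial in healthy lungs could matter to the statement that severe genotypes have almost no clearance. Section 9.3 also plans to read the absence of a mild-severe difference as evidence for another mechanism, so that contrast carries weight in either direction.

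**Working it through.** **Inputs (section 9.6).** Planned Ave60Clr: healthy 14.3 (SD 7.2), mild 3.6 (SD 2), severe 0.5 (SD 0.25). The mild value follows from the plan's own rule: 0.25 × 14.3 = 3.575, rounded to 3.6. Section 9.2 enrols 12 mild, 12 severe and 8 healthy. The plan gives no processing error, repeatability or reader variability, so there is no such figure to reproduce. The shifts below are assumptions.

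**How a processing error becomes clearance.** Retention R is the later count divided by the time-zero count, and clearance is 100 × (1 − R). A relative error e in the time-zero count alone, or the same e in all later images, moves clearance by about 100 × R × e. With R near 1, e of 0.5% to 1% gives about 0.5 to 1 point. An error that multiplies both counts equally cancels. An error of 1 point in one later image is diluted by averaging: if six 10-minute values enter the mean, 1/6 = 0.17 point.

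**Size against the planned values.**
- Mild minus severe: 3.6 − 0.5 = 3.1. Then 0.5/3.1 = 16% and 1/3.1 = 32%.
- Severe mean: 0.5/0.5 = 1 and 1/0.5 = 2 times the mean.
- Severe SD: 0.5/0.25 = 2 and 1/0.25 = 4 SDs.
- Healthy minus mild: 14.3 − 3.6 = 10.7. Then 0.5/10.7 = 5% and 1/10.7 = 9%.

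**Consequence if there were no true mild-severe difference.** Simulated pooled two-sample t-test, two-sided 0.05, 12 per group, 40,000 runs. The table gives the percentage of runs declared significant:

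| Assumed shift (points) | SDs 2 and 0.25 (as planned) | Both SDs 2 | Both SDs 0.25 |
|---|---|---|---|
| 0 | 6.4% | 5.0% | 5.0% |
| 0.25 | 8.1% | 5.9% | 65.1% |
| 0.5 | 14.6% | 9.3% | 99.7% |
| 1.0 | 38.8% | 21.3% | 100% |
| 2.0 | 90.2% | 65.1% | 100% |

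The last column needs a mild-group SD of 0.25, which is not what section 9.6 assumes.

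**Consequence if the planned difference is real.** With SDs 2 and 0.25 and 12 per group, t-test power is 99.8% with no shift, 98.7% with 0.5 point against the effect and 92.8% with 1 point against it.

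**Limit of this check.** Aim 1 specifies ANOVA with Tukey-Kramer, not a two-sample t-test. Its pooled error includes the healthy SD of 7.2. With 8, 12 and 12 participants, that test declared the full 3.1 difference significant in about 31% of 20,000 simulated runs. With the same SDs, a shift of 1 point alone would be declared less often than that. For Aim 1 the table therefore illustrates sensitivity and does not forecast the planned p-value. Bias in the estimated means and confidence intervals does not depend on the test. Aims 2 and 3 do use independent t-tests, but on change scores, whose SDs the plan does not state.

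**The case against.** The strongest reply is that the method leaves little room for an analyst's judgement. The transmission scan is taken before the radioaerosol is inhaled (table of procedures, section 4.1), so it holds no clearance information. Alignment uses physical markers whose positions are inked on the skin. Retention is a ratio to the participant's own time-zero activity, so a misplaced boundary shared by all images largely cancels. Averaging dilutes isolated errors. A full 1-point bias would need an error at time zero, or a uniform error in all later images, that also differs by genotype. The documents show no route to that. This all stands, and it reduces the likely size. It does not close the gap: the scan precedes inhalation, but the plan does not say when, by whom or how the regions are set on it.

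Some stronger readings are tempting and unsupported:
- **Processing differences are as large as the severe-group values.** No document gives their size. Only the conditional statement holds.
- **Regions are drawn by hand.** The text says that they are assigned from the transmission scan, without saying whether manually or automatically.
- **The analyst is unmasked because the treatment is open label.** Section 6.2 concerns assignment and gives no reason for its N/A. On readers the plan is silent.
- **Outlier judgement could decide the result.** Section 9.1 runs the analysis with and without extreme points, which largely answers this.

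The subject numbers and restricted access to identifiers in 11.9.1 are part of a solution. However, investigators keep access, and the numbers are not assigned to scan files. That the study is small and phase I limits the urgency, but the remedy is correspondingly small.

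**Conclusion.** The concern holds as a gap in protection. It is not a demonstrated bias. Group is known from recruitment, the direction is predicted, the outcome and a covariate both depend on image processing, and the plan describes no masking, automation or quality control of that processing.

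The size is unknown. The 0.5-to-1-point range rests on an assumed relative count error of about 0.5% to 1% that differs between groups and does not cancel. A shift of that size could distort the severe-group estimate and its comparison with zero. It would not by itself produce the planned mild-severe difference, and it would matter little against the planned healthy-mild difference. If the planned difference is real, power in a direct two-sample t-test would stay above 90%. The main exposure is an exaggerated or spurious mild-severe difference when the true one is small. Sample size, alpha and planned tests are unaffected. This is a cheap improvement that should be made.

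**What to change.** In section 6.2, replace the masking entry with a statement that treatment is open label but scan processing is masked to group:
- scan files carry the study number only;
- the existing analyst is not told the genotype group and sets regions and alignment by one fixed, written procedure;
- regions, alignment and any outlier flags are locked before group labels are merged.

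Amend 11.9.1 so that the subject number covers scan files as well as samples. If processing is already automated or masked, a sentence saying so would settle the point.

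The cost is a coding step and a lock step, with no extra reader, visit or participant. Masking of healthy versus PCD may be imperfect because scans can reveal disease. The mild-versus-severe comparison is the one best protected.
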